8.1.5. Expectedness

The PI will be responsible for determining whether a Grade III to V adverse event (AE) is expected or unexpected. An AE will be considered unexpected if the nature, severity, or frequency of the event is not consistent with the risk information previously described for the study intervention.

8.1.6. Follow-up of Adverse Events

Grade III to V AEs including local and systemic reactions not meeting the criteria for SAEs will be captured in the study record. Information to be collected includes event description, time of onset, clinician’s assessment of severity, relationship to study product (assessed only by those with the training and authority to make a diagnosis), and time of resolution/stabilization of the event. Grade III to V AEs occurring while on study must be documented appropriately regardless of relationship. All Grade III to V AEs will be followed to adequate resolution. Grade III to V AEs and SAEs will be collected between Day 1 and Day 29 (completion of study).

Any medical condition that is present at the time that the participant is screened will be considered as baseline and not reported as an AE.

Changes in the severity of an AE will be documented to allow an assessment of the duration of the event at each level of severity. AEs characterized as intermittent require documentation of onset and duration of each episode.

The PI or study coordinator will record all reportable Grade III or V events with start dates occurring after IP treatment is initiated until the last day of study participation. At each study visit, the investigator will inquire about the occurrence of AE/SAEs since the last visit. Events will be followed for outcome information until resolution or stabilization.

All enrolled subjects who have received CD24Fc or placebo will be evaluated for safety with the laboratory assays done at each visit as outlined in section 7.2. Safety will be assessed by vital signs, hematology, and chemistries. Vital signs will include pulse, blood pressure, respiratory rate, and oxygen saturation. The severity of signs, symptoms, and AEs will be determined by using CTCAE V5.0. The CD24Fc infusion will be administered over a minimum of 1 hour.

Subjects will be monitored after infusion is completed for 2 hours, and repeat vital signs and laboratory results will be ascertained as needed based on reported symptoms.

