8. ADVERSE EVENTS AND SERIOUS ADVERSE EVENTS

8.1. Adverse Events

8.1.1. Definition of Adverse Events

Adverse event means any untoward medical occurrence associated with the use of an intervention in humans, whether or not considered intervention-related. Since the clinical study has the target population as hospitalized patients with COVID-19 diagnosis and requiring oxygen support, the Grade III to V adverse events will be collected and reported in this study.

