8.1.3. Criteria for Determining the Severity of Adverse Events

AEs not listed in the CTCAE 5.0 version table can be classified into grades 1-5 with reference to the following table.

Grade	CTCAE
1	Asymptomatic or mild; only clinical or diagnostic observations; no intervention required
2	Moderate: Small, local, or non-invasive measures are required; age-related instrumental daily life activities (ADL) are limited *.
3	Serious or medically significant but not immediately life-threatening: hospitalization or lengthening of hospital stay required; disability, limited autonomic ADL **.
4	Life-threatening: urgent measures are needed. Intervention indicated to prevent permanent impairment, persistent disability or death.
5	deaths related to adverse events

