8.2. Adverse Event Reporting

Grade III to V AEs occurring from the time of treatment through the end of study will be documented, recorded, and reported. The Investigator will evaluate Grade III to V AEs with respect to **Severity** (intensity or grade) and **Causality** (relationship to study agent and relationship to research). The investigator will record nonserious adverse events and report them to the sponsor in a timely manner.

Grade III or V laboratory abnormalities that are gradable per the CTCAE v5.0 will be recorded as AEs or SAEs. All other laboratory abnormalities without clinical significance will not be recorded as AEs or SAEs. Grade III to V laboratory abnormalities that require medical or surgical intervention must be recorded as an AE or SAE if applicable. Laboratory assessments that are associated with signs and/or symptoms must be recorded as an AE or SAE if they meet the definition. If a diagnosis is clinically evident, the diagnosis, rather than the individual signs and symptoms or lab abnormalities will be recorded as the AE.

Grade I or II adverse events that worsen to grade III or V during the study will be captured. Their start date will be the day the adverse events worsen to grade III or V.

Events will be summarized on the basis of the date of onset for the event. A treatment-emergent adverse event will be defined as any new or worsening adverse event that begins on or after the date of treatment until study completion. Summaries (number and percentage of subjects) of treatment-emergent adverse events will be provided at study completion.

At each contact with the subject as outlined above in the study activities table, information regarding Grade III or V AEs will be elicited by appropriate questioning and examinations and will be immediately documented in the subject's medical record. Medical records will be reviewed in a timely manner by the research team. The onset date, the end date, the severity of each reportable Grade III to V event, and the Investigator's judgment of the AEs relationship to CD24Fc will also be recorded.

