8.5. Infusion Reaction Management

No infusion reactions were observed in Phase I, Phase IIa, and Phase II expansion cohort clinical trials. However, administration of any recombinant protein may induce infusion reactions. CD24Fc includes the Fc portion of human IgG1. After targeted binding, CD24Fc can induce FcγR cross-linking, which is related to infusion reactions that may occur during some treatments.

Possible infusion reactions during or 2 hours after the infusion include, for example, changes in vital signs, fever, dyspnea, hypotension, systemic or facial edema, nausea, chills, changes in mental state, urticaria, or vomiting.

The following procedures are designed to closely monitor, manage and mitigate any possible infusion reactions:

- In this study, CD24Fc must be administered in hospital. During the administration of CD24Fc, the clinical condition of the subject must be closely monitored.
- The infusion time is at least 60 minutes. Researchers are allowed to reduce the IV rate and extend the infusion time based on the infusion response. If severe infusion

reactions occur, such as severe hypotension and hypoxemia, the infusion should be stopped.

- Provide supportive treatment based on clinical indications and the intensity of the infusion reaction, including oxygen supplementation, diphenhydramine, acetaminophen, ibuprofen, IV corticosteroids (ie, hydrocortisone), and intravenous fluid replacement.
- During CD24Fc administration, bedside first aid equipment, cardiopulmonary resuscitation life support equipment and drugs (eg, epinephrine) must be prepared in order to cope with possible hypersensitivity reactions, severe infusion reactions and / or cytokine release.

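### Grade I–II infusion reactions are not recorded as adverse events, so the all-grade infusion-reaction rate cannot be compared between arms

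*Combined protocol and SAP*

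**What the plan says.** Section 8.1.1 notes that the patients are in hospital and on oxygen, and concludes that "the Grade III to V adverse events will be collected and reported in this study". Section 8.1.6 applies the same floor expressly to reactions: "Grade III to V AEs including local and systemic reactions not meeting the criteria for SAEs will be captured in the study record". Section 8.2 admits a lower-grade event only if it progresses: "Grade I or II adverse events that worsen to grade III or V during the study will be captured". Its onset is then dated to the day it worsened.

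Section 8.5 deals with infusion reactions. It reports that "No infusion reactions were observed in Phase I, Phase IIa, and Phase II expansion cohort clinical trials", but adds that the Fc portion of the molecule gives a mechanism by which they could occur. It continues: "Possible infusion reactions during or 2 hours after the infusion include, for example, changes in vital signs, fever, dyspnea, hypotension". The list goes on to edema, nausea, chills, altered mental state, urticaria and vomiting. The section asks for close observation during dosing and describes supportive measures, but contains no recording rule. Section 8.1.6 sets the observation period: "Subjects will be monitored after infusion is completed for 2 hours".

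Section 10.4.4 tabulates recorded adverse events by arm and summarizes vital signs, ECGs and laboratory results. No table of infusion reactions is planned.

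**The concern.** The reason given for the floor is background illness. That is sensible for four weeks of follow-up in severely ill inpatients. It is weaker for the roughly three hours around one blinded infusion, because the saline arm measures the background over the same window.

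Safety is part of the primary objective (section 2.1), and 270 patients is far more than the randomized Phase I (40) and Phase IIa (24) studies described. If few or no infusion reactions appear in the tables, a reader could take this as support for the statement in 8.5 that none have been seen, when the milder ones were never collected. The definition of a treatment-emergent event in 8.2 names no grade, so the resulting table could be mistaken for an all-grade one.

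**Working it through.** The plan gives no figure to reproduce here, so the check is of what the floor does to the count.

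**Inputs**
- Patients treated with CD24Fc: n = 135 (synopsis, Accrual Objective).
- True any-grade infusion-reaction rate r: not in the documents; assumed, shown as a range.
- Share of reactions at Grade III or higher, s: not in the documents; assumed, shown as a range.

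**Formulas**
- Reactions occurring = n × r.
- Reactions recorded under the floor = n × r × s.
- Chance that none is recorded = (1 − r × s)^n.
- Chance of none with all-grade recording = (1 − r)^n.

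Example with r = 5%, s = 10%: 135 × 0.05 = 6.75 occur; 135 × 0.005 = 0.68 are recorded; 0.995^135 = 0.51; with all grades recorded, 0.95^135 = 0.001.

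| r | Occurring | Recorded, P(none): s = 5% | s = 10% | s = 25% | P(none), all grades |
|---|---|---|---|---|---|
| 2% | 2.7 | 0.14, 87% | 0.27, 76% | 0.68, 51% | 6.5% |
| 5% | 6.75 | 0.34, 71% | 0.68, 51% | 1.69, 18% | 0.1% |
| 10% | 13.5 | 0.68, 51% | 1.35, 26% | 3.38, 3.3% | <0.1% |
| 20% | 27 | 1.35, 26% | 2.7, 6.5% | 6.75, 0.1% | <0.1% |

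**Which rows are plausible**
- Earlier CD24Fc exposures: 30 in Phase I (40 less 10 on placebo, since 6 placebo subjects are given as 60.0%), 18 in Phase IIa, and 20 in the expansion cohort (section 1.13). Total 68, with no infusion reactions reported. The one-sided 95% upper bound is 1 − 0.05^(1/68) = 4.3%.
- Section 1.11 counts 32 patients at 480 mg or above. None in 32 gives 1 − 0.05^(1/32) = 8.9%.
- The 2% and 5% rows are therefore the relevant ones. The higher rows show how the result moves; they are not forecasts.

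**Effect of such a floor on the sponsor's own data**
- Phase I (section 1.8.1): 6 + 2 + 3 + 2 + 3 + 2 = 18 of 40 subjects had a treatment-emergent event, 12 of them on CD24Fc.
- All events were mild to moderate except one severe headache on placebo. Reading mild-to-moderate as Grade I–II, a Grade III floor keeps 1 of the 18 subjects and 0 of the 12 on CD24Fc.
- These were adverse events of all kinds, not infusion reactions, so they illustrate the filter and do not estimate s.

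**The case against.** **The floor is deliberate and reasoned, and serious reactions are still captured.** This stands. Nothing in the text is self-contradictory, and any reaction of Grade III or higher is recorded.

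**Other data catch part of what is lost.** This also stands, in part. Temperature, blood pressure, heart rate and respiratory rate are taken before infusion and 60±10 minutes after it starts (7.1.4, 7.2.2). An ECG follows at 2 hours (7.1.8). Concomitant medications are collected (7.1.3) and summarized by randomized arm (10.3.3). So it would be wrong to infer that milder reactions leave no trace: fever, hypotension or a drug given for a reaction may appear. But the scheduled reading falls near the end of the infusion, later ones are taken as needed, nothing is labelled as a reaction, and vital signs cannot show urticaria, chills, nausea or vomiting.

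**Section 8.2 may already ask for more.** It says "The investigator will record nonserious adverse events and report them to the sponsor in a timely manner" without naming a grade. The sentence sits in a paragraph about Grade III–V events and is not a clear all-grade rule.

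**Stronger readings that the documents do not support**
- A reader might infer that the trial will report almost no reactions whatever the true rate. The table contradicts this: at a 20% rate and a 25% Grade III+ share, 6.75 are expected on record and the chance of none is 0.1%.
- A reader might infer from 8.1.3, where Grade 2 reads "Moderate: Small, local, or non-invasive measures are required", that any reaction handled with simple supportive measures falls below the floor. That table covers only events missing from CTCAE 5.0, and 8.1.6 grades severity by CTCAE itself, which the documents do not reproduce. The grade of a given sign cannot be settled from that table.
- A reader might take the listed signs as expected. Section 8.5 calls them possible, and the earlier record of none in 68 argues against high rates, although those were healthy volunteers and transplant patients rather than patients with COVID-19.

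**Conclusion.** The point holds in a limited form. Under 8.1.1, 8.1.6 and 8.2, Grade I–II infusion reactions are not recorded as adverse events, so the all-grade rate cannot be estimated or compared between arms from the 10.4.4 tables. A low count there would not show that reactions are rare. If 0 of 135 were recorded, the one-sided 95% upper bound of 1 − 0.05^(1/135) = 2.2% would apply to Grade III+ reactions only.

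The size depends on two assumed quantities. With a 10% Grade III+ share, the chance that none is recorded is 51% at a 5% rate and 76% at a 2% rate, against 0.1% and 6.5% with all-grade recording. A larger share shrinks the gap: at 25% the chances are 18% and 51%. This is an inexpensive improvement to safety data collection. It does not touch the efficacy analysis and is not an error that invalidates the plan.

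**What to change.** - **8.1.1, 8.1.6 and 8.2:** add one recording exception. Any sign listed in 8.5, of any grade, from the start of infusion to 2 hours after its end, is recorded in both arms, together with any slowing or stopping of the infusion.
- **10.4.4:** add a by-arm table of infusion reactions by grade.
- **Elsewhere:** keep the Grade III floor for all other events. No treatment or infusion rule changes.
- **While editing:** 8.1.6 and 8.2 alternate between Grade III to V and Grade III or V. Taken literally the second omits Grade IV, so the wording should be reconciled.

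**Cost:** one short eCRF page per patient, within observation that 8.1.6 already requires. Some background fever or dyspnea will be recorded as well, but in both blinded arms, so the comparison with saline allows for it.

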8.2. Adverse Event Reporting

Grade III to V AEs occurring from the time of treatment through the end of study will be documented, recorded, and reported. The Investigator will evaluate Grade III to V AEs with respect to **Severity** (intensity or grade) and **Causality** (relationship to study agent and relationship to research). The investigator will record nonserious adverse events and report them to the sponsor in a timely manner.

Grade III or V laboratory abnormalities that are gradable per the CTCAE v5.0 will be recorded as AEs or SAEs. All other laboratory abnormalities without clinical significance will not be recorded as AEs or SAEs. Grade III to V laboratory abnormalities that require medical or surgical intervention must be recorded as an AE or SAE if applicable. Laboratory assessments that are associated with signs and/or symptoms must be recorded as an AE or SAE if they meet the definition. If a diagnosis is clinically evident, the diagnosis, rather than the individual signs and symptoms or lab abnormalities will be recorded as the AE.

Grade I or II adverse events that worsen to grade III or V during the study will be captured. Their start date will be the day the adverse events worsen to grade III or V.

Events will be summarized on the basis of the date of onset for the event. A treatment-emergent adverse event will be defined as any new or worsening adverse event that begins on or after the date of treatment until study completion. Summaries (number and percentage of subjects) of treatment-emergent adverse events will be provided at study completion.

At each contact with the subject as outlined above in the study activities table, information regarding Grade III or V AEs will be elicited by appropriate questioning and examinations and will be immediately documented in the subject's medical record. Medical records will be reviewed in a timely manner by the research team. The onset date, the end date, the severity of each reportable Grade III to V event, and the Investigator's judgment of the AEs relationship to CD24Fc will also be recorded.

8.3. Serious Adverse Event Reporting

The study clinician will immediately report to the sponsor any serious adverse event, whether or not considered study intervention related, including those listed in the protocol or investigator brochure and must include an assessment of whether there is a reasonable possibility that the study intervention caused the event. Study endpoints that are serious adverse events (e.g., all-cause mortality) must be reported in accordance with the protocol unless there is evidence suggesting a causal relationship between the study intervention and the event (e.g., death from anaphylaxis). In that case, the investigator must immediately report the event to the sponsor.

All Grade V event (death) should be reported as SAE to CRO and sponsor in a timely manner.

All serious adverse events (SAEs) will be followed until satisfactory resolution or until the site investigator deems the event to be chronic or the participant is stable. Other supporting

documentation of the event may be requested by the study sponsor and should be provided as soon as possible.

The study sponsor will be responsible for notifying the Food and Drug Administration (FDA) of any unexpected fatal or life-threatening suspected adverse reaction as soon as possible, but in no case later than 7 calendar days after the sponsor's initial receipt of the information. In addition, the sponsor must notify the FDA and all participating investigators in an Investigational New Drug (IND) safety report of potential serious risks, from clinical trials or any other source, as soon as possible, but in no case later than 15 calendar days after the sponsor determines that the information qualifies for reporting.

The Medical Monitor will advise the Sponsor regarding the safety of the study participants as well as the continuing safety and scientific validity of the trial. The Medical Monitor may also review the results of any planned analysis, if applicable. If the data analysis shows significant findings with regards to safety, the Medical Monitor may recommend modification of the protocol, Informed Consent, and/or monitoring of the study. In these cases, the regulatory authorities and local review committees may be notified. The Medical Monitor may also stop the study for reasons of safety.

8.4. Reporting of Pregnancy

Pregnancy itself is not an AE. However, complications of pregnancies are AEs and may be SAEs. Pertinent obstetrical information of all pregnancies will be reported to the MM. The participant will be advised to notify her obstetrician of study agent exposure.

Pregnancy outcome data (e.g., delivery outcome, spontaneous, or elective termination of the pregnancy, presence of absence of birth defects, congenital abnormalities, or other complications) will be reported to the MM.

8.5. Infusion Reaction Management

No infusion reactions were observed in Phase I, Phase IIa, and Phase II expansion cohort clinical trials. However, administration of any recombinant protein may induce infusion reactions. CD24Fc includes the Fc portion of human IgG1. After targeted binding, CD24Fc can induce FcγR cross-linking, which is related to infusion reactions that may occur during some treatments.

Possible infusion reactions during or 2 hours after the infusion include, for example, changes in vital signs, fever, dyspnea, hypotension, systemic or facial edema, nausea, chills, changes in mental state, urticaria, or vomiting.

The following procedures are designed to closely monitor, manage and mitigate any possible infusion reactions:

- In this study, CD24Fc must be administered in hospital. During the administration of CD24Fc, the clinical condition of the subject must be closely monitored.
- The infusion time is at least 60 minutes. Researchers are allowed to reduce the IV rate and extend the infusion time based on the infusion response. If severe infusion

reactions occur, such as severe hypotension and hypoxemia, the infusion should be stopped.

- Provide supportive treatment based on clinical indications and the intensity of the infusion reaction, including oxygen supplementation, diphenhydramine, acetaminophen, ibuprofen, IV corticosteroids (ie, hydrocortisone), and intravenous fluid replacement.
- During CD24Fc administration, bedside first aid equipment, cardiopulmonary resuscitation life support equipment and drugs (eg, epinephrine) must be prepared in order to cope with possible hypersensitivity reactions, severe infusion reactions and / or cytokine release.

9. DATA MANAGEMENT

9.1. Data Collection and Management Responsibilities

Data collection is the responsibility of the clinical trial staff at the site under the supervision of the site investigator. The investigator is responsible for ensuring the accuracy, completeness, legibility, and timeliness of the data reported.

All source documents should be completed in a neat, legible manner to ensure accurate interpretation of data.

Data will be recorded in an electronic case report form (eCRF) using the secure electronic database. The data system includes password protection. The data entered will include but not be limited to clinical findings and observations, laboratory and test data, hospital medical records, physician or office charts, physician or nursing notes, recorded data from automated instruments, x-rays, etc.

9.2. Study Records Retention

Study documents should be retained for a minimum of 2 years after the last approval of a marketing application in an International Conference on Harmonisation (ICH) region and until there are no pending or contemplated marketing applications in an ICH region or until at least 2 years have elapsed since the formal discontinuation of clinical development of the study intervention. These documents should be retained for a longer period, however, if required by local regulations. No records will be destroyed without the written consent of the sponsor, if applicable. It is the responsibility of the sponsor to inform the investigator when these documents no longer need to be retained.

